4.2 METHOD OF TREATMENT ASSIGNMENT

Study patients will be assigned to study treatment cohort based on locally determined BRAF^{V600} disease status. Patients with BRAF^{V600} mutation-positive disease will be assigned to treatment with cobimetinib plus atezolizumab and vemurafenib in Cohort 2. As per the Dear Investigator Letter dated 9 July 2019, no new patients will be enrolled into Cohort 1. Ongoing patients in Cohort 1 may continue study treatment as per protocol, according to investigator's medical judgement.

4.3 STUDY TREATMENT

Cobimetinib and atezolizumab are the investigational medicinal products (IMPs) in Cohort 1 and cobimetinib, atezolizumab and vemurafenib are the IMPs in Cohort 2.

In this protocol, "study treatment" refers to the combination of treatments assigned to patients as part of this study (i.e. atezolizumab and cobimetinib in Cohort 1, and cobimetinib, atezolizumab and vemurafenib in Cohort 2).

4.3.1 Study Treatment Formulation, Packaging and Handling

4.3.1.1 Cobimetinib

Cobimetinib will be supplied by the Sponsor as 20-mg, film-coated, immediate-release tablets.

For information on the formulation and handling of cobimetinib, see the pharmacy manual and the Cobimetinib Investigator's Brochure.

4.3.1.2 Atezolizumab

Atezolizumab will be supplied by the Sponsor as a sterile liquid in a single-use, 20-mL glass vial. The vial contains approximately 20 mL (1200 mg) of atezolizumab solution.

For information on the formulation and handling of atezolizumab, see the pharmacy manual and the Atezolizumab Investigator's Brochure.

4.3.1.3 Vemurafenib

Vemurafenib will be supplied by the Sponsor as 240-mg, film-coated tablets.

For information on the formulation and handling of vemurafenib, see the vemurafenib pharmacy manual and the Investigator's Brochure.

4.3.2 Study Treatment Dosage, Administration and Compliance

4.3.2.1 Study Treatment Dosage – Cohort 1

Patients in Cohort 1 will receive cobimetinib and atezolizumab in 28-day treatment cycles as outlined in [Table 2](#):

Table 2 Cohort 1 Treatment Regimen

Cobimetinib: 60 mg (three tablets of 20 mg each) orally (PO) once a day (QD) on Days 1–21 of each 28-day cycle.

Atezolizumab: 840 mg intravenously (IV) on Days 1 and 15 of each treatment cycle

Study treatment will be continued until investigator-determined disease progression according to RECIST v1.1, death, unacceptable toxicity, withdrawal of consent, or pregnancy, whichever occurs first. Clinically stable patients who have a favourable benefit-risk ratio may continue study treatment beyond progression per RECIST v1.1 if pseudoprogression due to the effects of immunotherapy is suspected to have occurred or if disease progression is limited to ≤ 3 intracranial lesions that can be controlled with SRT and if all of the criteria listed in Section [4.3.2.3](#) are met. No change to the administration of Cohort 1 study treatment is required during intracranial SRT (if applicable).

Study treatment will be discontinued in patients who continue treatment beyond disease progression per RECIST v1.1 if clinical deterioration because of disease progression occurs at any time subsequently or if persistent disease growth is confirmed on follow-up disease assessments performed approximately four weeks later (or sooner if necessary e.g., due to clinical progression). The disease status of patients who continued study treatment and underwent intracranial SRT will be determined by the investigator according to RECIST v1.1 modified by excluding any treated lesions from the sum of largest diameters from baseline onwards.

Cases of overdose, medication error, drug abuse, or drug misuse, along with any associated adverse events, should be reported as described in Section [5.3.5.12](#).

Guidelines for dosage modification and treatment interruption or discontinuation for Cohort 1 patients who experience adverse events are provided in Section [5.1.6.1](#) and in the respective Investigator's Brochures.

4.3.2.2 Study Treatment Dosage – Cohort 2

Patients in Cohort 2 will receive vemurafenib, cobimetinib and atezolizumab in 28-day treatment cycles. Treatment will include a 28-day run-in period wherein patients will receive vemurafenib and cobimetinib only. Upon completion of the 28-day run-in period, atezolizumab will be added to their treatment regimen.

Study treatment administration in Cohort 2 is outlined in [Table 3](#):

Table 3 Cohort 2 Treatment Regimen

Cobimetinib	Run-in Period (Cycle 1)	
	Days 1-21	60 mg (three tablets of 20 mg each) PO QD
	\geq Cycle 2	
	Days 1-21	60 mg (three tablets of 20 mg each) PO QD
Vemurafenib	Run-in Period (Cycle 1)	
	Days 1-21	960 mg (four 240-mg tablets) PO twice daily (BID)
	Days 22-28	720 mg dose (three 240-mg tablets) PO BID
	\geq Cycle 2	
	Days 1-28	720 mg dose (three 240-mg tablets) PO BID
Atezolizumab	Run-in Period (Cycle 1)	
	Not administered during run-in period	
	\geq Cycle 2	
	Days 1 and 15	840 mg IV

Study treatment will be continued until investigator-determined disease progression according to RECIST v1.1, death, unacceptable toxicity, withdrawal of consent, or pregnancy, whichever occurs first. Clinically stable patients who have a favourable benefit-risk ratio may continue study treatment beyond progression per RECIST v1.1 if pseudoprogression due to the effects of immunotherapy is suspected to have occurred or if disease progression is limited to \leq 3 intracranial lesions that can be controlled with SRT and if all of the criteria listed in Section [4.3.2.3](#) are met. No change to the administration of cobimetinib and atezolizumab are required during intracranial SRT (if applicable). Caution should be used when administering vemurafenib during SRT and standard local treatment practices should be followed. It is recommended that vemurafenib be interrupted at last one day prior to SRT, and to resume at least 1 day

after the procedure. Please refer to Section 5.1.3.10 and to the Vemurafenib Investigator's Brochure for information regarding the risks associated with concomitant vemurafenib and radiation treatment.

Study treatment will be discontinued in patients who continue treatment beyond disease progression per RECIST v1.1 if clinical deterioration because of disease progression occurs at any time subsequently or if persistent disease growth is confirmed on follow-up disease assessments performed approximately four weeks later (or sooner if necessary e.g., due to clinical progression). The disease status of patients who continued study treatment and underwent intracranial SRT will be determined by the investigator according to RECIST v1.1 modified by excluding any treated lesions from the sum of largest diameters from baseline onwards.

Any overdose or incorrect administration of any of the study treatments and any adverse events associated with an overdose or incorrect study drug administration should be reported as described in Section 5.3.5.12.

Guidelines for dosage modification and treatment interruption or discontinuation for Cohort 2 patients who experience adverse events are provided in Section 5.1.6.2 and in the respective Investigator's Brochures.

4.3.2.3 Dosing of Study Treatment Beyond Disease Progression

Study treatment may be continued beyond progression per RECIST v1.1 if pseudoprogression due to the effects of immunotherapy is suspected to have occurred or if disease progression is limited to ≤ 3 intracranial lesions that can be controlled with SRT. Clinically stable patients in either cohort who have a favourable benefit-risk ratio may continue study treatment beyond progression per RECIST v1.1 for either reason if all of the following criteria are met:

- Clinically stable patient with evidence of clinical benefit and favourable benefit-risk ratio as determined by the investigator
- Absence of symptoms and signs (including laboratory values, such as new or worsening hypercalcemia) indicating unequivocal disease progression
- No decline in ECOG Performance Status that can be attributed to disease progression
- Absence of tumour progression at critical anatomical sites (e.g., leptomeningeal disease) that cannot be managed by protocol-allowed medical interventions
- Documented investigator/patient discussion of treatment options alternative to continuing study treatment at the time of RECIST v1.1-defined disease progression
- *Consultation with the Medical Monitor is advised*

Study treatment will be discontinued in any patient who continues treatment beyond disease progression per RECIST v1.1 if clinical deterioration because of disease progression occurs at any time or if persistent disease growth is confirmed on follow-up

disease assessments performed approximately four weeks later. Post-progression assessments may be conducted sooner if necessary e.g., due to clinical progression. The disease status of patients who continued study treatment and underwent intracranial SRT will be determined by the investigator according to RECIST v1.1 modified by excluding any treated lesions from the sum of largest diameters from baseline onwards.

Note that it is recommended that vemurafenib be interrupted at last one day prior to SRT, and to resume at least 1 day after the procedure.

4.3.2.4 Cobimetinib Administration

Cobimetinib should be taken at the same time every day. It can be taken with or without food. Cobimetinib should be swallowed whole with a glass of water and should not be chewed, cut, or crushed. If a daily dose of cobimetinib is missed (i.e. is not taken within 12 hours after the scheduled dosing time), or if vomiting occurs when the dose is taken, resume dosing with the next scheduled dose. Missed or vomited doses will not be made up.

4.3.2.5 Atezolizumab Administration

Administration of atezolizumab will be performed in a monitored setting where there is immediate access to trained personnel and adequate equipment and medicine to manage potentially serious reactions. For anaphylaxis precautions, see [Appendix 11](#). Atezolizumab infusions will be administered per the instructions outlined in [Table 4](#).

Table 4 Administration of First and Subsequent Atezolizumab Infusions

First Infusion	Subsequent Infusions

 No premedication is permitted prior to the atezolizumab infusion. 	
 If the patient experienced an IRR with any previous infusion, premedication with antihistamines, antipyretics, and/or analgesics (acetaminophen is prohibited for patients in Cohort 2 only - see Section 4.4.5) may be administered for subsequent doses at the discretion of the investigator.

 Vital signs (pulse rate, respiratory rate, blood pressure and temperature) should be measured within 60 minutes prior to the infusion. 	
 Vital signs should be measured within 60 minutes prior to the infusion.

 Atezolizumab should be infused over 60 (± 15) minutes. 	
 Atezolizumab should be infused over 30 (± 10) minutes if the previous infusion was tolerated without an IRR, or 60 (± 15) minutes if the patient experienced an IRR with the previous infusion.

 If clinically indicated, vital signs should be measured at 15, 30, 45 and 60 minutes (± 5 minutes for all timepoints) during the infusion and at 30 (± 10) minutes after the infusion. 	
 If the patient experienced an IRR with the previous infusion or if clinically indicated, vital signs should be measured during the infusion and at 30 (± 10) minutes after the infusion.

 Patients should be informed about the possibility of delayed post-infusion symptoms and instructed to contact their study physician if they develop such symptoms. 	

IRR = infusion-related reaction

Refer to the pharmacy manual for detailed instructions on drug preparation, storage and administration.

Guidelines for medical management of infusion-related reactions (IRRs) are provided in the Atezolizumab Investigator's Brochure.

No dose modification for atezolizumab is allowed.

4.3.2.6 Vemurafenib Administration

Vemurafenib should be taken in the morning and in the evening, approximately 12 hours later. Vemurafenib may be taken with or without food. Vemurafenib tablets should be swallowed whole with a glass of water and should not be chewed, cut, or crushed. If a dose of vemurafenib is missed (i.e., not taken within 12 hours after the scheduled dosing time), the patient should resume dosing with the next scheduled dose. Missed or vomited doses will not be made up.

Cobimetinib, atezolizumab, vemurafenib — F. Hoffmann-La Roche Ltd

65 / Protocol MO39136, Version 5.0

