In Cohort 2, treatment will begin with a 28-day run-in period wherein only vemurafenib and cobimetinib will be administered. During the run-in, cobimetinib will be administered at a dose of 60 mg QD Days 1-21. Vemurafenib will be administered at a dose of 960 mg BID Days 1-21 and at a dose of 720 mg BID Days 22-28. Following completion of the 28-day run-in, atezolizumab will be added to the combination for a final regimen of 60 mg cobimetinib QD (Days 1-21) plus 840 mg atezolizumab Q2W plus 720 mg vemurafenib BID (Days 1-28). These doses and schedule are also being assessed in the ongoing CO39262 study in advanced melanoma (see Section 1.3.2.4).

Cobimetinib is approved for administration at a dose 60 mg QD for Days 1-21 of each 28-day cycle in combination with vemurafenib for the treatment of BRAF^{V600} mutation-positive metastatic melanoma (see the current Cotellic Summary of Product Characteristics).

Atezolizumab will be administered at a fixed dose of 840 mg Q2W (840 mg on Days 1 and 15 of each 28-day cycle), which is an approved dosage for atezolizumab, as outlined in the prescribing information (also see Section 3.3.1).

Vemurafenib is approved for administration as monotherapy at a dose of 960 mg BID for the treatment of BRAF^{V600} mutation-positive advanced melanoma (see the current Zelboraf Summary of Product Characteristics).

Concomitant administration of cobimetinib 60 mg QD (Days 1-21), atezolizumab 800 mg IV (Days 1 and 15) and vemurafenib 720 mg QD (Days 1-28) following the 28-day run-in dosing and schedule as described above is being studied in Study GP28384 (see Section 1.3.2.3). Cobimetinib, atezolizumab and vemurafenib have been found to be safe and tolerable at these doses. Atezolizumab is formulated at a concentration of 60 mg/mL; thus, 800 mg corresponds to a volume of 13.33 mL. To ensure consistent, precise and clinically feasible administration in this study and Study CO39262 (see

Section 1.3.2.4), the volume has been rounded up to 14 mL, corresponding to a dose of 840 mg. This nominal increase is further supported by nonclinical dosing data and is not expected to be different from the 800 mg dose.

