4.3.2.7 Assessment of Compliance

To assess patient compliance with self-administration of cobimetinib in Cohort 1 and cobimetinib and vemurafenib in Cohort 2, patients will be required to record the time and date they took each dose in a medication diary; missed doses will also be recorded. Patients will be instructed to bring all unused study medication and their medication diaries at specified study visits (see [Appendix 1](#) [Cohort 1] and [Appendix 2](#) [Cohort 2]) for assessments of compliance.

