4.4.2.6 Medications Affecting the QT Interval – Cohort 2 Only

Caution should be exercised when Cohort 2 study treatment is co-administered with drugs that cause QT prolongation or cardiac arrhythmia, especially in patients with a pre-existing cardiac disease or ECG abnormality that may predispose them to cardiac dysrhythmia. Investigators should closely monitor patients who are on medications or

supplements that may affect the QT interval. Alternative treatment options for medications known to affect QT interval should be discussed with each patient prior to their enrollment in this study. Additional information is available at the following Internet site:

<https://crediblemeds.org/healthcare-providers/>

The effect of vemurafenib 960 mg BID on QT interval was evaluated in a multicentre, open-label, single-arm study in 132 previously-treated patients with BRAF^{V600} mutation-positive metastatic melanoma (Study NP22657). No large changes from baseline in mean QTc interval (i.e., > 20 ms) were detected in the study. However, vemurafenib is associated with concentration-dependent QT prolongation.

Although nonclinical studies showed a low potential for QT-interval prolongation with cobimetinib, no additive effect on QT-interval prolongation was observed when patients were treated with cobimetinib in combination with vemurafenib in Study GO28141. A combined cobimetinib and vemurafenib concentration-QTcF model (for which 433 patients contributed 1031 cobimetinib and vemurafenib observations) provided no evidence that cobimetinib prolonged QTcF interval when co-administered with vemurafenib.

4.4.3 Stereotactic Radiation in Cohort 2

Stereotactic radiation is permissible as described in Section 4.3.2.3. Due to vemurafenib radiation recall and radiation sensitization (see Section 5.1.3.10), caution should be used when giving vemurafenib concomitantly or sequentially with radiation treatment.

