5. ASSESSMENT OF SAFETY

5.1 SAFETY PLAN

The safety plan for patients in this study is based on clinical experience with cobimetinib, atezolizumab and vemurafenib in completed and ongoing studies. The anticipated important safety risks are outlined below (see Section 5.1.1 for cobimetinib, Section 5.1.2 for atezolizumab, Section 5.1.3 for vemurafenib, and Sections 5.1.4 and 5.1.5 for combination use). Cohort-specific guidelines for dose modifications and treatment interruption, as well as management of patients who experience specific adverse events, are provided in Section 5.1.6.

Measures will be taken to ensure the safety of patients participating in this study, including the use of stringent inclusion and exclusion criteria and close monitoring of patients during the study. Administration of atezolizumab will be performed in a monitored setting in which there is immediate access to trained personnel and adequate equipment and medicine to manage potentially serious reactions. Cobimetinib and vemurafenib will be dispensed with instructions for appropriate self-administration including handling of missed doses. Adverse events will be reported as described in Sections 5.2-5.7.

Patients with active infection are excluded from study participation. In the setting of a pandemic or epidemic, screening for active infections (including SARS-CoV-2) prior to and during study participation should be considered according to local or institutional guidelines or guidelines of applicable professional societies (e.g., American Society of Clinical Oncology or European Society for Medical Oncology).

Severe SARS-CoV-2 infection appears to be associated with a CRS involving the inflammatory cytokines IL-6, IL-10, IL-2, and IFN- γ (Merad and Martin 2020). If a patient develops suspected CRS during the study, a differential diagnosis should include SARS-CoV-2 infection, which should be confirmed or refuted through assessment of exposure history, appropriate laboratory testing, and clinical or radiologic evaluations per investigator judgment. If a diagnosis of SARS-CoV-2 infection is confirmed, the disease should be managed as per local or institutional guidelines.

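### The vemurafenib missed-dose window is as long as the dosing interval, so the protocol text guarantees no minimum gap between two doses

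*Protocol*

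**What the plan says.** Protocol Section 4.3.2.6 gives the routine schedule: "Vemurafenib should be taken in the morning and in the evening, approximately 12 hours later". It then defines a missed dose: "If a dose of vemurafenib is missed (i.e., not taken within 12 hours after the scheduled dosing time"). After a missed dose the patient picks up at the next scheduled one, and missed or vomited doses are not replaced.

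Section 4.3.2.4 uses the same limit for once-daily cobimetinib, where a dose counts as missed if it "is not taken within 12 hours after the scheduled dosing time".

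For the Cohort 2 run-in, Section 3.3.2 gives the vemurafenib doses: "Vemurafenib will be administered at a dose of 960 mg BID Days 1-21 and at a dose of 720 mg BID Days 22-28". Table 3 continues 720 mg twice daily from Cycle 2, and Section 5.1.6.2 allows a reduction to 480 mg twice daily in the triplet period.

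Three other places bear on how the rule works in practice:

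- Section 4.3.1.3 points elsewhere for handling: "For information on the formulation and handling of vemurafenib, see the vemurafenib pharmacy manual and the Investigator's Brochure".
- Section 5.1 refers to patient instructions: "Cobimetinib and vemurafenib will be dispensed with instructions for appropriate self-administration including handling of missed doses".
- Section 4.3.2.7 requires a diary: "patients will be required to record the time and date they took each dose in a medication diary; missed doses will also be recorded".

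None of these, nor Section 4.3.2.2, Section 5.1.6.2 or the vemurafenib note in Appendix 2, states a minimum spacing between two vemurafenib doses.

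**The concern.** A missed-dose rule should stop a late dose from running into the next one. For a twice-daily drug, a 12-hour window cannot do that: nominally, a dose does not become missed until the following dose is due. The limit works for a once-daily drug but not for vemurafenib.

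What is at stake is tolerability and QT safety, not the efficacy analysis. Vemurafenib is self-administered at home, and Section 4.4.2.6 says that "vemurafenib is associated with concentration-dependent QT prolongation". Section 5.1.3.6 likewise describes the effect as depending on exposure. The scheduled ECGs in Appendix 2 (Day 15 of Cycles 1–4, then every three cycles) are recorded before the morning doses, so they are not timed to follow two closely spaced doses. The diary shows the spacing only afterwards, and the missed-dose rule does not exclude it.

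**Working it through.** The documents give no minimum gap, so there is no planned figure to reproduce. The check is direct arithmetic on the stated schedule.

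**Inputs.** Vemurafenib interval about 12 h and window 12 h (Section 4.3.2.6). Cobimetinib interval about 24 h and window 12 h (Section 4.3.2.4). Vemurafenib doses 960 mg and 720 mg twice daily (Table 3), reduced dose 480 mg twice daily (Section 5.1.6.2).

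**Guaranteed gap = interval − window.**

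| Drug | Window / interval | Guaranteed gap |
|---|---|---|
| Vemurafenib | 12/12 = 100% | 12 − 12 = about 0 h |
| Cobimetinib | 12/24 = 50% | 24 − 12 = 12 h |

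The vemurafenib interval is only approximate. If it runs from 11 to 13 h (assumed range), 11 − 12 = −1 h and 13 − 12 = +1 h. The window then closes anywhere from 1 h after to 1 h before the next dose is due.

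**Gap left by a late vemurafenib dose = 12 − lateness.**

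- 6 h late: 12 − 6 = 6 h.
- 9 h late: 12 − 9 = 3 h.
- 11.5 h late: 12 − 11.5 = 0.5 h.

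**Amount taken within 30 minutes when a dose is 11.5 h late.**

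- Cycle 1 Days 1–21: 2 × 960 = 1920 mg.
- From Cycle 1 Day 22: 2 × 720 = 1440 mg.
- On the reduced dose: 2 × 480 = 960 mg.

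Each equals the planned daily total, so only the timing changes.

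**Gap guaranteed by a shorter window (assumed values, 12 h interval).** A 4 h window leaves 12 − 4 = 8 h, a 6 h window leaves 6 h, and an 8 h window leaves 4 h.

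**Dose lost for each additional dose counted as missed.** The denominator is the planned dose per cycle. This is an assumption, because SAP Section 5.6.1 lists dose intensity without a formula.

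- Planned Cycle 1: 21 × 2 × 960 + 7 × 2 × 720 = 40,320 + 10,080 = 50,400 mg.
- Planned later cycle: 28 × 2 × 720 = 40,320 mg.
- One dose on Cycle 1 Days 1–21: 960/50,400 = 1.9%.
- One dose on Cycle 1 Days 22–28: 720/50,400 = 1.4%.
- One dose in a later cycle: 720/40,320 = 1.8%. Four doses: 4 × 720/40,320 = 7.1%.

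**The case against.** The best counter-argument is that the scenario depends on reading one sentence of Section 4.3.2.6 apart from another. The opening sentence can be taken as a spacing instruction, and two doses half an hour apart would not meet it. The rule also defines a missed dose; it does not tell anyone to take a dose 11.5 h late. Patients act on the dispensing instructions rather than on the protocol, and those may be tighter.

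The safety link is thin as well. If the preceding dose was on time, the late dose follows it by 12 + 11.5 = 23.5 h, so cumulative intake never runs ahead of schedule. Section 4.4.2.6 reports no large mean QTc change at 960 mg twice daily. QTcF entry limits (Section 4.1.2), scheduled ECGs (Appendix 2) and QTcF action rules (Appendix 13, Table 11) are in place.

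Much of this stands, and it is why the point is minor. It does not remove the defect in the text. The opening sentence sets the routine, while the missed-dose rule is tied to the scheduled time, and nothing shifts the schedule or sets a gap after a late dose. Placing the cut-off at 12 h implies that anything earlier is acceptable. If the unseen instructions are tighter, the protocol should be aligned with them; if they repeat the protocol, the gap reaches patients.

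**Conclusion.** The concern holds for the protocol text. As written, the vemurafenib rule guarantees about 0 h between doses, against 12 h for cobimetinib under the same limit.

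The severity is minor. The conclusion rests on a literal reading of Section 4.3.2.6 and on a nominal 12 h interval. The pharmacy manual, Investigator's Brochure and dispensing instructions were not available. The documents do not say how often doses would fall this close together or what that would do to QTc, so no harm is shown. There is no consequence for sample size, endpoints or the primary analysis.

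**What to change.** Shorten the vemurafenib window in Section 4.3.2.6 so that it closes well before the next scheduled dose, using the limit in the Investigator's Brochure or label. If neither gives one, 6 h is a workable example. Carry the same limit into the patient instructions and diary. Classification of medication errors can stay with the existing definitions in Section 5.3.5.12.

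The cost is one sentence in an amendment or site letter, plus the updated patient material, with no extra visits. There are two downsides:

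- A few more doses will count as missed. For 1 to 4 such doses in one later cycle (assumed range), vemurafenib dose intensity in that cycle falls by 1.8% to 7.1%.
- A dose taken after the shorter window closes departs from the rule. If the site classes it as a medication error, Section 5.3.5.12 requires an Adverse Event eCRF entry and Section 5.4 requires reporting within 24 hours. How many such cases would arise is unknown.
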